8.4.7.1 ESA Rescue (Optional)

Starting at Week 6, subjects in both treatment arms will be allowed (although will not be required) to have their Hb rescued with ESA therapy per the local standard of care. Drug product and supplies for ESA rescue will not be provided by the Sponsor.

If possible, a subject on vadadustat should be on a maximum dose of vadadustat for 2 weeks prior to ESA rescue. A subject on darbepoetin alfa may rescue with another ESA per the standard of care. To qualify for ESA rescue, a subject must fulfill BOTH of the following:

- The subject has experienced worsening of the symptoms of anemia (eg, fatigue, weakness, shortness of breath, chest pain, confusion, or dizziness) compared with Baseline
- The subject's Hb is <9.0 g/dL

However, in the event the subject does not meet the above criteria for ESA rescue, ESA rescue is permitted when medically necessary at the discretion of the Investigator. Reasons for ESA use will be captured in the appropriate CRF.

The ESA rescue therapy should be administered as per the local institution's guidelines and per the approved local product label. While receiving ESA rescue therapy, subjects must temporarily discontinue taking study medication (vadadustat or darbepoetin alfa). Hemoglobin will be monitored throughout the study at scheduled visits as defined in the Schedule of Activities using HemoCue, and ESA rescue treatment should be stopped when Hb is ≥ 9.5 g/dL. A minimum interval must be observed prior to restarting vadadustat after the last dose of rescue medication, and treatment may be resumed after the following intervals:

- 2 days after last dose of epoetin rescue
- 7 days after last dose of darbepoetin alfa rescue
- 14 days after last dose of methoxy polyethylene glycol-epoetin beta rescue.

Following ESA rescue, the study medication should be resumed at the same dose as previously used or one dose higher and adjusted according to the Dose Adjustment Algorithm (Section 8.4.4, Dosing and Dose Adjustment Guidelines). If a subject's study medication has been temporarily interrupted for more than 60 days, the Investigator should contact the Medical Monitor before resuming study medication.

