8.4.7.2 Red Blood Cell Transfusion (Optional)

Investigators will use their local institution's transfusion guidelines when determining whether to transfuse a study subject. In general, in the event of an acute or severe loss of blood, a RBC transfusion should be administered as clinically indicated. In less severe instances but where there may be worsening of anemia or moderate to severe symptoms of anemia, RBC transfusions are permitted at the discretion of the Investigator given the medical necessity. Reasons for RBC transfusion will be captured in the appropriate CRF (e.g., worsening anemia due to CKD, blood loss, surgery, etc.). Study medication (vadadustat or darbepoetin alfa) may be continued during the RBC transfusion period.

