8.5.2 Erythropoiesis-stimulation Agents

Non-protocol ESAs are prohibited from Randomization until the end of the study, unless the subject is receiving ESA rescue therapy, interrupts study treatment for other reasons, or permanently discontinues study medication. Reasons for ESA use will be captured in the appropriate CRF (e.g., adverse event, inadvertent administration, etc.).

Concomitant use of an ESA with study medication is strictly prohibited.

In the setting of ESA rescue therapy, the initial dose of ESA rescue therapy may be administered on the same day as the last vadadustat dose prior to vadadustat dose interruption (see [Section 7.5.5.1, Temporary Interruption of Study Medication](#)) if deemed medically necessary at the discretion of the Investigator. Guidelines for ESA administration as rescue therapy are provided in [Section 8.4.7.1, ESA Rescue](#).

All efforts will be made to avoid inadvertent administration of ESAs resulting from following routine ESA hemodialysis protocols (e.g., dialysis center ESA protocols for subjects on hemodialysis). If ESA is inadvertently administered to subjects actively receiving vadadustat treatment, vadadustat treatment will be stopped and the event will be reported as a protocol deviation.

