11.2 Study Analysis Populations

The following analysis populations will be used in this study:

- Randomized population: defined as all randomized subjects
- Full analysis population: defined as randomized subjects receiving 1 or more doses of study medication and had at least one Hb assessment during the primary efficacy evaluation period. This population will be analyzed based upon the randomized treatment.

- Per protocol (PP) population: defined as all randomized subjects who received study medication (vadadustat or darbepoetin alfa) during the primary evaluation period, had at least 2 Hb assessments during the primary evaluation period, and received no rescue therapy (with ESA or RBC transfusion) in the 8 weeks prior to the evaluation period, and have no protocol deviations affecting the primary endpoint analyses. Protocol deviations leading to exclusion from the per protocol population will be specified prior to database lock on a blinded basis and recorded in a separate document.
- Safety population: defined as all subjects who received at least 1 dose of study medication. This population will be analyzed based upon the actual treatment received.

Efficacy analyses will utilize the randomized, full analysis, and PP populations while safety analyses (including MACE) will utilize the randomized population.

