11.6.1.2 Sensitivity Analyses of Primary Efficacy Endpoint

The following sensitivity analyses will be conducted:

- Primary analysis will be repeated using the full analysis population.

- Primary analysis will be repeated using only subjects with available Hb data during the primary evaluation period, ie, excluding subjects with no available data during the primary evaluation period.
- Primary analysis will be repeated using the PP population with the actual treatment received.
- Primary analysis will be repeated with alternate approaches to imputation of missing data as described in the SAP.
- Primary analysis will be repeated with imputation of data which may have been affected by a subject's having received any form of rescue (transfusion or ESA). Details are provided in the SAP.

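### The per protocol population excludes rescue in the 8 weeks before Weeks 24-36 but not rescue, transfusion or non-protocol ESA inside that window, and ESA use not labelled rescue can escape the imputation analysis as well

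*Protocol*

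**What the plan says.** All references are to Protocol Amendment 7.

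- **PP membership (11.2).** A subject must have "received study medication (vadadustat or darbepoetin alfa) during the primary evaluation period, had at least 2 Hb assessments during the primary evaluation period", must have "received no rescue therapy (with ESA or RBC transfusion) in the 8 weeks prior to the evaluation period", and must "have no protocol deviations affecting the primary endpoint analyses". The list of excluding deviations is to be fixed on a blinded basis in a separate document.
- **ESA rescue (8.4.7.1).** "Starting at Week 6, subjects in both treatment arms will be allowed" it, and the investigator may also use it at discretion when the criteria are not met. "While receiving ESA rescue therapy, subjects must temporarily discontinue taking study medication (vadadustat or darbepoetin alfa"), and it is resumed afterwards.
- **Transfusion (8.4.7.2).** Permitted at the investigator's discretion. "Study medication (vadadustat or darbepoetin alfa) may be continued during the RBC transfusion period".
- **Non-protocol ESA (8.5.2).** Prohibited after randomization unless the subject is on ESA rescue, "interrupts study treatment for other reasons, or permanently discontinues study medication". Section 7.5.5.2 expects standard care, ESAs included, to resume after permanent discontinuation.
- **Analyses.** The primary analysis (11.6.1.1) uses the randomized population and keeps Hb values taken after rescue and after discontinuation. Section 11.6.1.2 repeats it in PP by actual treatment received. A separate bullet there imputes data that may have been affected by a subject's "having received any form of rescue (transfusion or ESA"). Section 11.6.2 also uses PP for the key secondary endpoints.

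**The concern.** The PP exclusion stops at the point where the endpoint begins. Rescue at Week 18 removes a subject. Rescue at Week 26 does not, although it acts on the Hb values that are averaged. An ESA is the comparator class, so a vadadustat subject given one in Weeks 24-36 contributes Hb that vadadustat did not produce, and a PP result that keeps such subjects is weaker support for noninferiority.

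A second gap concerns labels. Section 8.5.2 separates rescue from other permitted ESA use, while the imputation analysis names rescue only. Read as written, ESA taken during an interruption for other reasons, or after permanent discontinuation, is caught by neither the PP exclusion nor the imputation.

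The protocol itself fixes the PP rescue window and leaves only the deviation list to a later document, so an analysis plan that follows the protocol inherits the gap.

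**Working it through.** **1. The plan's own figure.** Inputs from section 11.1.1: SD 1.5 g/dL, margin -0.75 g/dL, 925 per arm, true difference 0, two-sided 95% CI.

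- SE = 1.5 × √(2/925) = 0.0697; CI half-width = 1.96 × 0.0697 = 0.137 g/dL.
- Power = Φ(0.75/0.0697 - 1.96) = Φ(8.79) > 0.9999, which agrees with the stated figure of more than 90%. About 85 per arm would give 90%.

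No stated figure is wrong. The problem is one of definition.

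**2. Who stays in PP under the text.** Each row assumes at least 2 Hb values in Weeks 24-36.

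| Subject | Study drug in window | Rescue in prior 8 weeks (about Weeks 16-24) | Deviation | In PP |
|---|---|---|---|---|
| ESA rescue at Week 18, drug resumed | yes | yes | no, permitted | no |
| ESA rescue at Week 26 | yes, before or after rescue | no | no, permitted | yes |
| Transfusion at Week 26, drug continued | yes | no | no, permitted | yes |
| Interrupts for another reason in the window, takes non-protocol ESA | yes, any dose suffices | no | no, permitted | yes |
| Inadvertent ESA while on vadadustat | yes | no | yes (8.5.2) | may be removed through the deviation list |

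Analysis by actual treatment received does not change this. Section 11.6.1.2 does not say that a subject who is later rescued changes group.

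**3. How much of the average is affected.** Section 9.3.5 schedules Hb at Weeks 24, 28, 32 and 36. After rescue at Week 26, 3 of the 4 values follow it.

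**4. Possible shift in the PP difference.** The documents give no in-window rescue rate, arm imbalance or Hb uplift, so all of these are assumed. With the same uplift in both arms:

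shift = uplift × (vadadustat share - darbepoetin share)

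- Net excess 5%, uplift 0.5: 0.05 × 0.5 = +0.025 g/dL (3.3% of the margin).
- Net excess 15%, uplift 1.0: 0.15 × 1.0 = +0.15 g/dL (20% of the margin, about one CI half-width).
- Equal shares: 0.
- Wider assumptions, from 5% versus 2% with uplift 0.5 up to 20% versus 5% with uplift 1.5, give +0.015 to +0.225 g/dL.

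**5. When this could change a PP conclusion.** If the true difference were exactly -0.75, the chance that the PP interval clears the margin is Φ(shift/SE - 1.96):

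- shift 0: 2.5%
- shift 0.025: Φ(0.36 - 1.96) = 5.5%
- shift 0.15: Φ(2.15 - 1.96) = 57.6%

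Without contamination the interval passes when the estimate is at least -0.75 + 0.137 = -0.613. With a shift of 0.15 it passes when the uncontaminated estimate is at least -0.763. The conclusion differs only between those two values, far from the planned difference of 0.

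**6. What exclusion does.** Power is not at risk: at 500 per arm, SE = 1.5 × √(2/500) = 0.095 and power is still above 0.9999. Exclusion does select, however. If excluded subjects average g below the others, removing them raises the arm mean by share × g. With the same 5-15% net excess and an assumed g of 0.5-1.0 g/dL, the difference moves by a further +0.025 to +0.15 g/dL, also toward noninferiority.

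**The case against.** The strongest reply is that exclusion is a poor remedy on its own. The standard criteria in 8.4.7.1 start rescue below 9.0 g/dL and stop it at 9.5 g/dL, while the target begins at 10.0 g/dL. A subject rescued by those criteria probably has a low window mean even after rescue, so keeping that subject may be more conservative than deleting a treatment failure. This stands as a cost of the fix (step 6). It does not justify the current rule, which deletes the same kind of subject at Week 18 and keeps one at Week 26. It is also weaker for discretionary rescue and for ESA after discontinuation, which are not tied to those thresholds.

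Second, the protocol gives the rescue question to another analysis. Section 11.5 promises sensitivity analyses of the impact of rescue, and the last bullet of 11.6.1.2 has no 8-week limit, so it covers labelled rescue inside the window. That stands. What remains is ESA use not labelled rescue. The analysis plan might define this more widely, but the protocol wording does not require it to.

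Third, a subject who stops vadadustat at Week 25 and moves to an ESA is a weak example. The end-of-treatment visit includes a blood count, but visits afterwards are flexible and Hb is not on the list of preferred assessments (7.5.5.4). Few ESA-affected values may exist, although 11.5 asks such subjects to continue planned visits. Rescued or transfused subjects who stay on schedule are the clear case.

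A reader might also infer that the PP analysis is biased in favour of vadadustat. The documents do not support that. The same rule and the same access to rescue apply to darbepoetin, and the shift can be zero or reverse.

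**Conclusion.** The gap is real on the text. PP keeps subjects given permitted ESA rescue, transfusion or non-protocol ESA inside Weeks 24-36, and permitted ESA use not labelled rescue can fall outside the imputation analysis too. It favours vadadustat only if in-window use, or its effect on Hb, is greater in that arm. Under an assumed net excess of 5-15% and uplift of 0.5-1.0 g/dL the PP difference shifts by +0.025 to +0.15 g/dL.

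It would be tempting to conclude that the noninferiority claim itself is compromised, or that PP was the designated safeguard against crossover to the comparator class. Neither follows. The noninferiority decision rests on the randomized population, where post-rescue data are included by design. The protocol gives PP no such role and lists it as one of five sensitivity analyses. The defect is confined to supportive analyses, so it is moderate rather than something that must be fixed before the primary result can be read.

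**What to change.** 1. **Section 11.2.** Replace the rescue clause of the PP definition with: *no rescue therapy (ESA or RBC transfusion) and no non-protocol ESA from 8 weeks before the start through the end of the evaluation period*.
2. **Weeks 40-52.** Add a matching rule for the PP analysis of the key secondary endpoints in that period. The present definition has no rescue rule near it.
3. **Section 11.6.1.2, last bullet.** Widen the trigger for imputation to: *RBC transfusion or any non-protocol ESA as listed in 8.5.2, whether or not labelled rescue*.
4. **Interpretation.** State that PP is to be read beside the widened imputation analysis, because excluding treated subjects removes low-Hb treatment failures and can itself favour noninferiority.

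The cost is a few lines of text. The case report form already captures reasons for ESA use and for transfusion (8.4.7.1, 8.4.7.2, 8.5.2). The PP population becomes somewhat smaller, with no meaningful loss of power. The selection effect in item 4 is the real downside, which is why items 1 and 3 should be made together. No clinical rule on rescue needs to change.

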11.3 Analysis of Demographic and Pretreatment Variables

Descriptive statistics will be generated for demographic and pretreatment variables for each analysis population defined in [Section 11.2, Study Analysis Populations](#).

Medical history terms will be coded using the Medical Dictionary for Regulatory Activities (MedDRA) and summarized by System Organ Class and Preferred Term for each treatment group based on the safety population.

11.4 Disposition of Subjects

The number and percentage of subjects randomized and included in each analysis population will be summarized by treatment and overall. Reasons for excluding subjects from the analysis populations will be presented in a by-subject listing.

The number of randomized subjects who completed each period of study medication treatment (correction, maintenance, and long-term treatment), discontinued from study medication early, and completed or discontinued from the study and reasons for discontinuation will be summarized by treatment group and overall.

11.5 Missing Data

Subjects who stop study medication treatment after randomization and prior to completion of the study should continue with planned study visits and assessments unless they withdraw consent for participation in the study. Similarly, subjects will continue with study medication and study procedures following the initiation of rescue therapy, with the exception that the subjects must discontinue taking study medication while receiving an ESA rescue therapy. Treatment with study medication should be resumed after an appropriate interval following the ESA rescue therapy as described in [Section 8.4.7, Rescue Therapy](#). Data will continue to be collected following initiation of the rescue therapy as per the study Schedule of Activities.

All data collected during the study, including at any point after the initiation of rescue therapy as well as after early discontinuation of study medication treatment, will be used for the primary analysis as well as main analyses of all efficacy endpoints. Sensitivity analyses will be performed to assess an impact of rescue therapy on study conclusions.

In the primary analysis of the primary efficacy endpoint, all available qualifying Hb measurements during the pretreatment period and during the primary evaluation period

(Weeks 24-36) will be used to calculate an average Hb during each period, respectively, for each subject. For any subject with no available Hb measurements during the primary evaluation period, multiple imputations will be used to impute the change from Baseline value (details are provided in the SAP). In an analogous manner, an average Hb will be calculated for the secondary evaluation period (Weeks 40-52) for each subject. Given the design of this study where the subjects will continue to be assessed after early study medication discontinuation, it is expected that there will be only a minimal amount of missing data and the primary analysis should not be substantially affected by the imputation.

All data pertaining to the MACE endpoint collected at any point during the study, both during study medication treatment and post study medication treatment discontinuation, and regardless of the rescue therapy, will be used for the primary analysis of the MACE endpoint and its individual components.

Unless stated otherwise in the SAP, missing data for all other secondary efficacy and safety endpoints will not be imputed and the analysis will be based on observed data. For certain responder-type binary endpoints, subjects with no available data will be classified into one of the categories as described in the relevant sections of the SAP.

11.6 Efficacy Analyses

The primary efficacy endpoint as well as all key and other secondary endpoints will be summarized using descriptive statistics by treatment group, as well as by study visit and/or analysis period as appropriate. Mean values of Hb as well as selected other efficacy parameters will be plotted across study visits/periods by treatment group.

11.6.1 Analysis of Primary Efficacy Endpoint

The primary efficacy endpoint is defined as the mean Hb change from Baseline (mean pretreatment Hb) to the mean Hb from Weeks 24 to 36 (inclusive).

11.6.1.1 Primary Analysis of Primary Efficacy Endpoint

The primary analysis will use an analysis of covariance (ANCOVA) with multiple imputation, stratified by the randomization strata and using Baseline Hb as the covariate. A 2-sided, 95% confidence interval (CI) will be calculated for the difference between treatment groups (vadadustat minus darbepoetin alfa). Noninferiority of vadadustat will be established if the lower limit of this CI is ≥ -0.75 g/dL.

The primary analysis will be performed using the randomized population and the assigned treatment as described in [Section 11.2, Study Analysis Populations](#). All data collected during the study for subjects included in the randomized population at the time of analysis, including data collected at any point after the initiation of rescue therapy as well as after early discontinuation of study medication treatment, will be used for the primary analysis. Missing data will be handled using multiple imputation methodology as described in the SAP.

11.6.1.2 Sensitivity Analyses of Primary Efficacy Endpoint

The following sensitivity analyses will be conducted:

- Primary analysis will be repeated using the full analysis population.

- Primary analysis will be repeated using only subjects with available Hb data during the primary evaluation period, ie, excluding subjects with no available data during the primary evaluation period.
- Primary analysis will be repeated using the PP population with the actual treatment received.
- Primary analysis will be repeated with alternate approaches to imputation of missing data as described in the SAP.
- Primary analysis will be repeated with imputation of data which may have been affected by a subject's having received any form of rescue (transfusion or ESA). Details are provided in the SAP.

11.6.2 Secondary Efficacy Analyses

Secondary efficacy endpoints analyses will be performed using the randomized and full analysis populations and the assigned treatment as described in [Section 11.2, Study Analysis Populations](#). Analysis for the key secondary efficacy endpoints will be repeated using the PP population with the actual treatment received.

11.6.2.1 Key Secondary Efficacy Analyses

Mean change in Hb value between Baseline and the secondary evaluation period (Weeks 40-52) will be analyzed using the same methodology as specified for the primary efficacy endpoint. Sensitivity analyses similar to those of the primary efficacy endpoint will be performed and details will be provided in the SAP.

11.6.3 Subgroups

Analyses of the primary efficacy endpoint and key secondary efficacy endpoints will also be performed using the randomized and full analysis populations, using the assigned treatment, for subgroups based on the following:

- Hb stratification level
- NYHA CHF stratification level
- Due to use of different target Hb levels in the US vs. non-US, the endpoints will also be analyzed for subsets based on the target Hb level:
 - the U.S. subset will be assessed due to the target Hb range being 10.0-11.0 g/dL in the U.S.
 - the combined EU and ROW (non-US) will be assessed since the target Hb range is 10.0-12.0 g/dL in these two Regions
- Geographic region (US, EU, ROW)
- Age
- Gender
- Race

11.7 Safety Analyses

All analyses of safety data will use the randomized population.

11.7.1 Analysis of MACE and Expanded MACE components

The primary safety endpoint, time to the first adjudicated MACE, will be analyzed as [date of the first MACE minus the date randomization +1]. A MACE is defined as all-cause mortality, non-fatal myocardial infarction, or non-fatal stroke. Subjects who have not experienced a MACE by study closure will be censored on the date of their last study assessment. The hazard ratio (vadadustat/darbeoetin alfa) and its 95% confidence interval will be obtained from a stratified Cox proportional hazards model. As this study has not been designed to provide a standalone assessment of MACE, this analysis will be considered a descriptive analysis. A similar analysis as described for the primary analysis of the MACE endpoint will be performed with censoring of subjects 4 weeks following discontinuation of study medication if they did not have a MACE prior to that time.

An additional analysis as described for the primary analysis of the MACE endpoint will be performed with censoring at time of chronic dialysis initiation for subjects who have progressed to chronic dialysis and who did not have a MACE prior to that time.

The following safety endpoints will also be summarized using time to event methods as for MACE:

1. Individual components (all-cause mortality, non-fatal myocardial infarction, non-fatal stroke) of MACE
2. Thromboembolic events (defined as arterial thrombosis, DVT, PE, or vascular access thrombosis)
3. Hospitalization for heart failure
4. Expanded MACE, defined as all-cause mortality, non-fatal myocardial infarction, non-fatal stroke, hospitalization for HF, or thromboembolic event

For these endpoints the incidence ("yes"/"no") of the endpoint will be presented for each treatment arm. Kaplan-Meier curves will be presented for each endpoint as the time of endpoint free survival (ie, time until endpoint or death).

The primary MACE analysis will be based upon all events that accrue over the 2 NDD-CKD studies (Studies AKB-6548-CI-0014 and AKB-6548-CI-0015) (see [Section 11.1.2, Sample Size for the Primary Safety Endpoint](#)).

The SAP for this pooled MACE assessment in NDD-CKD subjects provides details of the primary analyses for MACE, for individual components of MACE, and for an expanded version of MACE. Details of sensitivity analyses and subgroup analyses are also provided in the MACE SAP.

